The first session will be scheduled by the research coordinator; subsequent appointments will be made directly between the NP's and the patient. The first session must be scheduled between 14 and 21 days after the participant's date of surgery. After the initial call, NP's will be responsible for tracking and competing intervention calls.

Intervention Protocol

Participants randomized to MI+GOW will receive the intervention from a single provider ([name]). Of note, participants will have all opioids and additional pain medications prescribed by their surgeon during the study. [name] will only be providing advice regarding participants' opioid medications. Content of the MI call is detailed in the Intervention section above. Treatment engagement is defined as participation in >50% of phone sessions. Treatment initiation is defined as participation in at least 1 phone session.

Longitudinal Follow-up

Scheduling Follow-Up Assessments

Electronic surveys will be sent out automatically based on confirmed dates of surgery. Distribution of online assessments will occur via the REDCap survey invitations calendar defined in the Longitudinal Observation Project, beginning seven days after the date of surgery. A patient's official date of surgery will be entered into the "Pre-Surgery Call" instrument in REDCap during the Pre-Surgery call, and confirmed during the Post-Surgery call. The study team member may verify the date of surgery and time of discharge in EPIC and record it on the "Post-Surgery Call" instrument.

Medical Chart Review

Research team member will review the patient's medical record for information required on the case report form.

Compliance Monitoring

Participant compliance with follow-up assessments will be assessed weekly through an automated reporting dashboard. Patients failing to complete two consecutive follow-up assessments be contacted

MAP-Pain Standard Operating Procedures

by the research coordinator, to encourage continued participation. The coordinator may offer to limit the participant's follow-up to monthly surveys, to maintain follow-up data collection for the participant.

Survey Frequency Reduction

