To reduce instances of participants lost to follow-up or withdrawing, the coordinator can reduce the frequency of participant surveys from weekly to monthly. To complete this, the coordinator will check the "Monthly Surveys Only" checkbox in the "Coordinator Controls" instrument of the Longitudinal Observation REDCap project, and save the instrument.

Lost to Follow-up Participants

A participant is considered "Lost to Follow-up" if they have not completed a follow-up assessment for two months, and cannot be reached by the research coordinator. The Research coordinator will attempt to call the participant three times before declaring them lost to follow-up, leaving a voicemail message. If a participant has alternative numbers listed (like a spouse or relative), those numbers should be attempted many times before inactivating the participant.

If the coordinator has determined the participant is lost to follow-up, the coordinator will mark the participant status as "Inactive" in the Coordinator Controls Instrument of Longitudinal Observation REDCap. The coordinator will also input the date of last contact with the participant, and select "Lost to follow-up" as the reason for withdrawal. Participant notes may be used to elaborate on the circumstances of the participant's withdrawal.

Patient Withdrawn or Study Completion

If a patient is withdrawn from the study, the study coordinator will mark the participant status as "Inactive" in the Coordinator Controls Instrument of Longitudinal Observation REDCap and document the date of the last contact and reason for withdrawal. The study coordinator will also input the date of last contact with the participant, and select "Lost to follow-up" as the reason for withdrawal. Participant notes may be used to elaborate on the circumstances of the participant's withdrawal.

Weekly and Monthly Surveys

Weekly Assessments

The following assessments will be completed weekly via online assessment up to 6 months, and then monthly up to 12 months for all participants.

1. Weekly Pain and Opioid Questionnaire (WPOQ, combined into one instrument with BPI)
2. Modified Brief Pain Inventory-II (BPI, combined with WPOQ into one instrument)

Monthly Assessments up to 6 months

The following assessments will be completed monthly via online assessment up to 12 months for all participants.

1. Patient Health Questionnaire-9 (PHQ-9)

MAP-Pain Standard Operating Procedures

2. Common Opioid Misuse Measure (COMM)
3. PROMIS Measures

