Upon a patient being withdrawn or lost to follow-up, the study coordinator must also go into the REDCap instrument “Participant Entry” and switch the patient’s status to “Inactive.” At that point a warning message will automatically appear listing all of the future events for that participant, which the coordinator will then remove by clicking “Clean up Calendar Entries” under the project bookmark heading on the left side of the screen. Coordinator will also clean up calendar entries in the Calling Project for participants who have withdrawn or reached study completion.

Data Management

Data will be maintained on appropriate case report forms and participant questionnaires. Case Report Form data will be entered into a REDCap database.

Patient Identification Codes

Both Intervention and Observation arm participants will receive two unique codes identifying their records, saved as the “record_id” in both projects. In the Enrollment project, this code is a 4-digit number, assigned sequentially and automatically when the participant’s information is imported into the project (Example: 0000). In the Longitudinal observation project, the research coordinator assigns an alphanumeric code to serve as the participant’s record_id, consisting of their First and Last Initial, and the enrollment record_id (Example: AA-0000)

Tracking Events

Consent, Pre-Surgery, and Post-Surgery calls will be tracked in the REDCap Study Calendar, and are generated by completion of the brief eligibility screen, and manual scheduling by the research coordinator.

Online assessments will be distributed and tracked by the Longitudinal Event Calendar in the Longitudinal Observation REDCap Projects

Intervention calls are initially scheduled between the research coordinator, participant, and appropriate study team member. All subsequent calls will be independently scheduled and tracked by the NP and participant.

MAP-Pain Standard Operating Procedures

Hard-copy Data Storage

All data received or collected in paper form must be filed in lockable cabinets, and documented in the appropriate event of the REDCap Enrollment Project. Physical Okay to contact forms, Eligibility checklists, screening checklists, and consent forms must be filed in a binder and stored in lockable cabinets.

Okay to Contact Forms

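### Patients who are unreachable but have not refused follow-up are made Inactive and their future events removed, with no way back, so later opioid-use and COMM reports to month 12 are forgone

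*Protocol*

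**What the plan says.** The protocol section Lost to Follow-up Participants sets two conditions that must both hold. A participant is lost "if they have not completed a follow-up assessment for two months, and cannot be reached by the research coordinator". The coordinator must first "attempt to call the participant three times before declaring them lost to follow-up, leaving a voicemail message". Where other numbers are on file, "those numbers should be attempted many times before inactivating the participant". The section then reads: "If the coordinator has determined the participant is lost to follow-up, the coordinator will mark the participant status as" Inactive, in the Coordinator Controls instrument. It says nothing about removing events.

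Two sections are titled Patient Withdrawn or Study Completion. The later one, after Censoring, goes further: "Upon a patient being withdrawn or lost to follow-up, the study coordinator must also go into the REDCap instrument" Participant Entry and set the status to Inactive. A warning then appears "listing all of the future events for that participant, which the coordinator will then remove", using a calendar clean-up function. Withdrawn and lost patients get the same treatment in this step.

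Under Tracking Events: "Online assessments will be distributed and tracked by the Longitudinal Event Calendar" in the longitudinal REDCap project. Scheduling Follow-Up Assessments says the surveys go out automatically.

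Two steps come before a patient is lost. Compliance Monitoring says: "Patients failing to complete two consecutive follow-up assessments be contacted" by the coordinator, who may offer monthly surveys. Participant Monitoring requires a check of active participants at least weekly, with reminder calls for missing assessments.

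For analysis, the protocol's section on missing data and non-adherence censors dropouts at their final observation and rules out imputation.

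**The concern.** A patient who stops answering has not withdrawn consent. The surveys are automated and online, so continuing to send them costs almost nothing, whereas the test of reachability is by telephone and made at about one point in time. Failing that test does not show that every later survey, over what may be many months, would go unanswered.

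If the invitations stop, the patient can supply no later opioid-use report and no later COMM score, and enters the time-to-cessation analysis as censored at the last report. If silence is related to continued opioid use or to recovery, that censoring is informative, and some of it could have been avoided. A patient inactivated before month 6 would receive neither the 6-month nor the 12-month assessment, the two follow-up surveys that carry a $20 reward.

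The two-month limit is also fixed in calendar time while survey frequency is not. It therefore stands for far fewer missed surveys once a patient is on a monthly schedule, including patients moved there as a retention measure under Survey Frequency Reduction.

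**Working it through.** **The plan's own figure.** The only related figure is under Enrollment Goals: 220 for the intervention arm allowing 10% censoring, and 558 for the observational arm allowing 15% attrition. The supplied text gives no hazard ratio, power or event count, so 220 cannot be reproduced. It is consistent with 198 / (1 − 0.10) = 220, but 198 is back-calculated here and not stated. No figure is given for loss to follow-up alone.

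**Do the surveys stop?**
- The removal instruction covers all listed future events.
- Tracking Events says the surveys are sent from the longitudinal event calendar.
- Clean-up of the Calling Project is named as an additional step, so the first removal appears to cover something other than those calls.
- Against this, Tracking Events also names a separate study calendar for coordinator calls, and the removal instruction does not say which calendar is cleaned.

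That the surveys stop is a strong inference from the text, not a statement in it.

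**How many missed surveys make two months?** Inputs:
- Weekly Assessments gives weekly surveys to month 6, then monthly to month 12.
- Alternating Monthly Assessments places the later surveys four weeks apart, at weeks 24, 28, ..., 52. I take the weekly phase as weeks 1 to 24.
- Two months is taken as 8.0 weeks, or 61/7 = 8.71 weeks. The counts are the same for both.

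Missed = surveys due after the last completed one and up to (last week + limit). Remaining = surveys due after that, to week 52.

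| Schedule | Last completed | Limit reached | Missed | Remaining |
|---|---|---|---|---|
| Standard | week 4 | week 12.0–12.7 | 8 | 19 |
| Standard | week 12 | week 20.0–20.7 | 8 | 11 |
| Standard | week 20 | week 28.0–28.7 | 5 | 6 |
| Standard | week 24 | week 32.0–32.7 | 2 | 5 |
| Standard | week 36 | week 44.0–44.7 | 2 | 2 |
| Monthly only | week 4 | week 12.0–12.7 | 2 | 10 |

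On a weekly schedule the limit takes eight missed surveys. On a monthly one it takes two.

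**Lead time for retention.** The Compliance Monitoring trigger is two consecutive misses.
- Weekly: 2 weeks after the last report, so 8.0 − 2 = 6.0 to 8.71 − 2 = 6.71 weeks before the limit.
- Monthly: 8 weeks after the last report, so 0 to 0.71 weeks before it.

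The weekly check under Participant Monitoring fills this gap. After a missed week-28 survey it gives about three to four checks before week 32.

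**Number of patients.** Planned censoring in the intervention arm is 220 × 0.10 = 22. The observational arm is under the same rule, and its planned attrition is 558 × 0.15 = 83.7, about 84. Neither figure is loss to follow-up alone: second surgery, complications, death and withdrawal can also end follow-up. If the plan's allowances hold, they are therefore upper limits. The documents give no rate at which silent patients resume.

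**Which outcomes are affected?** The intervention arm's primary endpoint is the first of two consecutive reports at or below baseline dose. A patient who met it before falling silent loses nothing on it. For the others, one isolated late report does not establish an event, unless the plan allows it to pair with the last report before the gap. The plan does not say. COMM scores need no pairing.

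**The case against.** The strongest reply is that this is ordinary practice: contact ends only after documented and repeated failure to reach the patient, and the sample size already allows for 10% censoring. Several stronger readings are tempting, and the documents do not support them.

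- A reader might infer that two months of silence, or two missed surveys, is enough for inactivation. It is not: the patient must also be unreachable after three calls and tries at any alternative numbers. A patient who answers is not lost.
- A reader might infer that outcome data are thrown away. The rule removes future events, and everything collected up to the last report stays in the analysis.
- A reader might take the end of the surveys as stated. It is inferred, as set out above.
- A reader might see a conflict between the two-miss trigger in Compliance Monitoring and the weekly check in Participant Monitoring. They work as successive tiers, and the weekly check already provides a call after one missed survey, so no new trigger is needed.
- A reader might put a number on the patients recoverable. Any such number needs a return rate that the documents do not give, and an assumption about how much of the 10% is loss to follow-up.
- A reader might infer that the rewarded surveys are never sent to any of these patients. A patient lost after month 6 has already been sent the 6-month one.

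It is also fair that the gain on the primary endpoint is limited, because two consecutive reports are needed and a long gap leaves the cessation time uncertain. What remains after all this is that patients who have not refused are closed out in the same way as those who withdrew, with no route back.

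**Conclusion.** The point holds as a cheap improvement to follow-up procedure, not as a flaw that undermines the trial. Following the protocol very probably ends automated surveys for unreachable patients who have not withdrawn consent, and nothing describes reactivation or later contact. The loss is of future reports only, mainly COMM scores to month 12 and late cessation times.

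Its size is unknown. It is at most 22 of 220 intervention patients if the plan's censoring allowance holds, and fewer once other causes and patients already at the primary endpoint are set aside. Any bias depends on silence being related to opioid use or recovery, which is plausible but not shown in the documents. The conclusion rests on reading the removed events as including the survey events.

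**What to change.** 1. In Lost to Follow-up Participants and in the later Patient Withdrawn or Study Completion section, limit removal of survey events to patients who withdraw consent for data collection.
2. For patients lost to follow-up, stop the reminder calls, leave the automated invitations on to week 52, and return the patient to active status on any response.
3. Reconcile the inactivation instructions. One section uses Coordinator Controls and mentions no event removal; the other uses Study Stop Point and Participant Entry and does remove events. The earlier Patient Withdrawn section also has the coordinator enter loss to follow-up as the reason for a withdrawn patient. Refusal and non-contact need separate codes for step 1 to work.
4. In the SAP, say whether reports on either side of a long gap count as consecutive, and how a cessation time inside the gap is handled, for example as interval-censored in a sensitivity analysis beside the planned log-rank and Cox analyses.

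The cost is SOP wording, a REDCap setting and a short SAP addition. The downside is some unanswered emails and some long gaps between reports.

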Study Title:

Motivational Interviewing and Guided Opioid Tapering Support to Promote Postoperative Opioid Cessation

NCT03659734

Document Date: 2/26/2019

Analytic Plan: Results of Cox and logistic regression analyses will be reported with and without stratification by gender. The intention-to-treat (ITT) analysis will include all patients with at least one set of follow-up data after randomization. We will examine the distribution of baseline covariates amongst groups to establish adequacy of randomization. We will use Kaplan Meier analysis and the log-rank test of significance to compare the groups at a two-sided a level=0.05, to identify a difference in time to opioid cessation. We will use Cox regression to adjust for potential confounders only if randomization is inadequate, and for surgery type. (Adequate randomization should adjust for confounding. In the event that the baseline covariate distribution amongst the groups are unbalanced, these specific covariates will be tested as potential confounders.) We will evaluate the effect of treatment group on time to opioid cessation. For sensitivity analyses, we will compare models from manual and automated selection techniques through AIC values. We will test for non-violation of the proportional hazards assumption and linearity assumptions of continuous predictors. Secondary outcomes include time to complete opioid cessation.

In a similar ITT analysis, we will compare the proportion of postoperative opioid misuse between groups, using the chi-square test. We will use logistic regression to characterize the effect of group on postoperative opioid misuse, with adjustment for confounders (only if randomization is inadequate) and surgery type. Sensitivity analyses will similarly compare -2 Log L scores of models. We will test linearity assumptions of significant predictors.

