Immediately after receiving (and if applicable, locking the consent form), the date of consent must be filled in COORD: Consent Call. The Baseline Questionnaire must be sent via REDCap by checking the correct box. Participants are encouraged to complete the Baseline Packet immediately. The research coordinator will schedule the Pre-Surgery for the first workday preceding their date of surgery, and confirm the pre-surgery call appointment with the participant. The coordinator will save the form to send the Baseline Packet URL-Link to the Participant, and schedule the pre-surgery call in the REDCap Calendar.

Pre-Surgical Assessment

Baseline Questionnaire Packet

After enrollment, participants will complete a pre-surgical questionnaire packet (AKA the Baseline Packet) via REDCap. Participants are given access to the Baseline Packet immediately after Electronic Consent is obtained and reviewed, and are encouraged to complete it immediately after receiving access.

Pre-surgical assessments in addition to Preoperative CHOIR are documented below:

1. Contact, surgical, and demographic information (labeled “Baseline Packet” in REDCap)
2. PHQ-9 – Patient Health Questionnaire-9
3. Baseline BPI-II – Modified Brief Pain Inventory-II including PAINMAP.
4. BPOQ - Baseline Pain and Opioid Questionnaire (Current opioid use and addiction susceptibility)
5. HADS – Hospital Anxiety and Depression Scale
6. TAPS - Tobacco, Alcohol, Prescription medications, and other Substance Tool
7. COMM – Current Opioid Misuse Measure
8. DSO - DSM-5 Opioids
 - a. Administered if COMM Total Score >9
9. BDI – Beck Depression Inventory-II

MAP-Pain Standard Operating Procedures

10. ACE- Adverse Childhood Event Questionnaire
 - a. Administered to Observation Participants only.
11. PROMIS Measures
 - a. PROMIS Bank v1.0- Depression
 - b. PROMIS Bank v1.0- Anxiety
 - c. PROMIS Bank v1.0- Sleep Disturbance
 - d. PROMIS Bank v2.0- Physical Function

Pre-Surgical Call Scheduling

Once consent is obtained, the research coordinator will schedule the Pre-Surgery Call with the participant. This call is to be scheduled the first workday prior to the participant's date of surgery. Unless a specific timeslot is requested by the participant, Pre-Surgery calls should be scheduled at 23:15 in the REDCap Calendar, and completed in the afternoon.

Pre-Surgical Call

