During the pre-surgery call, the coordinator will schedule the post-surgical call fourteen days after the participant’s date of surgery. Unless a specific timeslot is requested by the participant, Post-Surgery calls should be scheduled in the REDCap Calendar at 23:45 for observation participants, and 23:59 for intervention Participants.

Post-Surgical Call

Fourteen days after the participant’s date of surgery, the study coordinator will call the participant to confirm their date of surgery, the date and time they were discharged from the hospital, and verify if the participant has been prescribed and is still using opioid medications for surgical pain. The coordinator will call the patient five times, or until the patient picks up. If possible and necessary, the coordinator should leave a voicemail and specify the name of the patient, the purpose of the call, and leave a return name and number. If appropriate, the coordinator will randomize the study participant immediately after their call.

Randomization

During the Post-Surgical Call (Fourteen days after surgery) the research coordinator should verify whether or not the intervention participant in question has been prescribed and is still using opioid medications for surgical pain. Those who meet this criteria will be randomized to either the Motivational Interviewing and Guided Opioid Weaning intervention, or Enhanced Usual Care. Those who do not meet this criteria will be placed in the Observational arm of the study.

Participants are randomized in the Transfer to Longitudinal Instrument in the MAP-Pain Enrollment REDCap. Upon clicking the “Randomize” button, the coordinator will be prompted to select the surgery type (THR/TKR) and confirm the randomization. The participant will be randomized to “1” or “0”, denoting MI+GOW and EUC respectively. Once randomized, the participant cannot be moved to a different study group, so care must be taken to ensure participant is randomized correctly.

MAP-Pain Standard Operating Procedures

After random group assignment, the Transfer to Longitudinal instrument must be saved to transfer the participant's group assignment to the MAP-Pain: Longitudinal Observation REDCap project. The coordinator will send an email to the appropriate NP, to inform them of a newly randomized participant, and set up an appointment for MI+GOW or EUC sessions to begin.

Blinding and Randomization Methodology

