Randomization table was pre-generated using SAS. Randomization occurs using blocked, stratified randomization by operation. Randomization table was pre-generated onto spreadsheets, with rows hidden (in Excel). Each randomized patient will receive the next available row (unhidden by the coordinator at 14 days post-surgery for randomization as needed).

The PI will be blind to the patient's randomization status until completion of analyses. Due to the limitations of REDCap's randomization module, the research coordinator cannot be blinded to the randomization status of the participant.

Enhanced Usual Care (EUC)

Participants will receive phone calls matching the duration and frequency of MI+GOW calls. [name], NP will contact participants via phone to review one topic per call in this sequence: 1) standardized instructions on taking opioid medications after surgery, 2) avoiding medication mistakes, 3) alternative methods for pain management after orthopedic surgery, 4) understanding complementary and alternative medicine, 5) safe opioid use, 6) local mental health resources (including a suicide prevention hotline), 7) prescription drug abuse. She will briefly review patient education brochures in a didactic style without a tailored discussion. She will remind participants to complete REDCap assessments.

Intervention

The experimental intervention arm is Motivational Interviewing and Guided Opioid Weaning (MI+GOW). A pain medicine nurse practitioner ([name], NP) will administer MI+GOW. See table below for MI Components. The GOW protocol will be a 25% total daily opioid dose reduction every 7 days with opioid discontinuation 7 days after reaching 1 opioid pill per day. During phone sessions, patients will be monitored for worsening pain and opioid withdrawal through administration of the NRS and SOWS with the protocol specified in the "Guided Opioid Weaning" table below. Participants will be reminded that they can always use less opioids than recommended. Non-adherence is opioid use greater than previously recommended via the last phone call. During the randomization call, the first MI appointment should be scheduled by referring to [name]'s schedule.

Table MI Components

Principles	Strategies	Information Recorded by Interventionist	Information and Advice Offered in an MI-consistent manner (Elicit patient's knowledge, Provide advice, Elicit feedback)
------------	------------	---	---

MAP-Pain Standard Operating Procedures

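### The postoperative opioid dose before day-14 randomisation is not prespecified in the primary analysis or the balance check, which gives up power and leaves a chance dose imbalance uncorrected

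*SAP*

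**What the plan says.** The SAP's Analytic Plan names the test: "We will use Kaplan Meier analysis and the log-rank test of significance to compare the groups at a two-sided a level=0.05". On adjustment it says: "We will use Cox regression to adjust for potential confounders only if randomization is inadequate, and for surgery type". The trigger for anything beyond surgery type is a look at balance: "We will examine the distribution of baseline covariates amongst groups to establish adequacy of randomization", followed by "In the event that the baseline covariate distribution amongst the groups are unbalanced, these specific covariates will be tested as potential confounders". It gives no list of covariates, no time point and no threshold for imbalance.

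The protocol supplies the timing:

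- **Baseline.** Under Baseline Questionnaire Packet, "participants will complete a pre-surgical questionnaire packet (AKA the Baseline Packet) via REDCap". The packet includes a questionnaire on current opioid use. The primary outcome for the intervention trial (Primary Efficacy Outcome-Intervention Arm) is the first of two consecutive reports at or below the baseline opioid dose, which also presumes a pre-surgical value.
- **Randomisation.** Under Randomization, the day-14 call is to "verify whether or not the intervention participant in question has been prescribed and is still using opioid medications for surgical pain". As described, this is a yes/no check that records no dose. Blinding and Randomization Methodology stratifies by operation only.
- **Data already collected.** Under Scheduling Follow-Up Assessments, online surveys go out "beginning seven days after the date of surgery". Weekly Assessments lists a weekly pain and opioid questionnaire.

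**The concern.** By day 14 patients have had joint replacement and two weeks of postoperative opioids, so their pre-surgical values do not describe them at randomisation. The outcome is how long the postoperative dose takes to fall back to its pre-surgical level, so the dose just before assignment is close to the outcome's own starting value. For a patient who used no opioids before surgery, the pre-surgical dose is zero and cannot separate one such patient from another.

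That dose is not named in the strata, the log-rank test, the Cox model or the balance check. Two things are at stake. Omitting a strong prognostic factor from a time-to-event comparison pulls the hazard ratio toward 1 and lowers power. A chance difference in starting dose between the arms also passes into the estimate without correction. If dose were added only after an imbalance was noticed, or through the automated model selection in the SAP's sensitivity analyses, the adjustment would be driven by the data.

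**Working it through.** **1. The plan's own figure.** Enrollment Goals gives 220 for the intervention trial with 10% censoring, so 220 × 0.9 = 198 events. The supplied documents state no effect size or power, so 220 cannot be reproduced uniquely. By Schoenfeld's formula at two-sided 0.05, 198 events give 80% power at HR = exp[2 × (1.960 + 0.842)/√198] = 1.49, and 81% power at HR 1.5. I use HR 1.5 as an assumption consistent with that size. HR above 1 means faster cessation with MI+GOW.

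**2. Why dose is plausibly prognostic.** The Intervention section's taper is a "25% total daily opioid dose reduction every 7 days with opioid discontinuation 7 days after reaching 1 opioid pill per day". For a patient who adheres with no holds or increases, count weekly steps until D × 0.75^k ≤ 1, then add one week:

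| Pills/day | Steps to ≤ 1 | Weeks to stop |
|---|---|---|
| 2 | 3 | 4 |
| 4 | 5 | 6 |
| 8 | 8 | 9 |
| 12 | 9 | 10 |

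This concerns complete cessation in adherent MI+GOW patients only.

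**3. Power if the dose is known exactly.** Simulation assumptions: 110 per arm (1:1), exponential times, 10% censored, conditional HR 1.5, one standard-normal dose covariate (such as log dose), 2,000 runs per cell.

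| Log-hazard per SD of dose | Cessation HR per SD | Log-rank | Dose-adjusted Cox | Gain (points) |
|---|---|---|---|---|
| 0 | 1.00 | 83% | 83% | 0 |
| 0.25 | 0.78 | 77% | 82% | 5 |
| 0.50 | 0.61 | 70% | 84% | 14 |
| 0.75 | 0.47 | 55% | 81% | 26 |

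At HR 1.0, over dose effects from 0 to 1.0 per SD, rejection rates were 5.0–5.6% (log-rank) and 4.2–5.4% (adjusted). Both are nominal within simulation error.

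**4. Power if the dose is a proxy.** The covariate available is the last report before assignment. For many patients that is week 1, because the week-2 survey falls around the day-14 call. Two sets of runs of the same design, with assumed correlations between the report and the dose at randomisation, gave these gains in points:

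| Covariate | 0.3 per SD | 0.5 per SD | 0.7 per SD |
|---|---|---|---|
| Exact dose | 6 and 6 | 14 and 17 | 22 and 26 |
| Proxy, r = 0.7 | 3 and 3 | 6 and 6 | 8 and 11 |
| Proxy, r = 0.5 | 2 and 1 | 4 and 4 | 2 and 2 |

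The first figure in each cell comes from 500 runs, where one power estimate has a standard error of √(0.7 × 0.3/500) ≈ 2 points. Single cells should not be read more finely than that.

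**5. Chance imbalance.** The SE of a standardised mean difference is √(2/110) = 0.135. So P(|difference| > 0.1) = 46%, P(> 0.2) = 14% and P(> 0.25) = 6%. With a 0.2 SD imbalance and conditional HR 1.5, the average estimates were:

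| Log-hazard per SD | Unadjusted, MI+GOW on higher dose | Unadjusted, MI+GOW on lower dose | Adjusted |
|---|---|---|---|
| 0.50 | 1.31 | 1.56 | 1.52–1.53 |
| 0.75 | 1.21 | 1.51 | 1.51–1.52 |

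Without imbalance the unadjusted HR averages about 1.43 and 1.35 in these two rows. That part of the gap is the usual attenuation of a marginal hazard ratio.

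**The case against.** Several stronger readings are tempting, and the documents do not support them.

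- **That the SAP's balance check excludes this dose.** The SAP never defines its baseline covariates. In a trial randomised on day 14, a week-1 report is also pre-randomisation data. The protocol's usage makes the pre-surgical reading the natural one, but it remains an inference. What stands is that the dose is not specified.
- **That dose is the main driver of time to cessation.** No document says so. The taper arithmetic does not apply to enhanced usual care and assumes adherence to advice that patients may decline. The pain and withdrawal table can also hold or raise the dose. Moreover, the arithmetic describes complete cessation, a secondary outcome. For patients using opioids before surgery, the primary outcome depends on the excess over their own earlier dose, so the pre-surgical dose must be in the model too.
- **That the result would be invalid or biased.** Type I error is nominal, and chance imbalance does not bias a randomised comparison on average. The harm is to power and to the estimate in the one trial that is run.
- **That the full gain is available.** The larger figures assume an exactly measured, fully observed dose; a week-1 proxy recovers much less. No gain reaches the primary test unless the adjusted Cox test becomes that test.
- **That few patients would lack a report.** No completion rate is given, and the protocol plans for missed surveys.

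These objections reduce the claim but do not remove it. Prespecified adjustment for the outcome's own starting value is better than adjustment that waits for an imbalance to be seen. In the simulation it cost nothing when dose was not prognostic.

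**Conclusion.** The point holds as a matter of efficiency and prespecification, not validity. The postoperative dose before randomisation is a likely strong prognostic factor, a weekly report of it should already exist, and the plan assigns it no role.

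Under conditional HR 1.5, 110 per arm, 10% censoring and a dose effect of 0.3 to 0.7 log-hazard per SD, adjustment is worth about 5 to 25 power points with an exact dose. With a week-1 report correlated 0.5 to 0.7 with that dose, it is worth roughly 1 to 11 points. Hazard ratio, prognostic strength, correlation, equal allocation and complete covariate data are all assumptions, so the size cannot be tied to the planned power. That the weekly questionnaire yields a daily dose is inferred from the outcome definition, which needs reported doses to compare with baseline. The change should be made, but the trial can be interpreted without it.

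**What to change.** In the SAP's Analytic Plan:

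1. Prespecify three Cox covariates, whatever the observed balance: log(1 + total daily opioid dose) from the last weekly questionnaire completed before assignment (week 1, or week 2 if submitted before assignment); the pre-surgical opioid dose; and surgery type. Use them for both time to return to baseline dose and time to complete cessation.
2. Designate this adjusted Cox test as the primary treatment test, and report the log-rank test beside it.
3. Define baseline covariates by list and time point, and show the pre-randomisation dose by arm in the baseline table.
4. Use a missing indicator where no pre-randomisation report exists. This fits the protocol's rule against imputation, and the missingness precedes assignment.

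The cost is SAP wording, settled before anyone sees results by arm; no new data collection should be needed. There are two downsides. The hazard ratio becomes conditional on dose, and an unknown share of patients will have no pre-randomisation report, which reduces the gain.
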